	
b. Hemoglobin < 9 gm/dL, white blood count (WBC) count < 2500 mm³, neutrophil count < 1500 mm³, platelet count < 100 × 10³/ mm³
 
c. Evidence of hemoglobinopathy (including but not limited to sickle cell disease, thalassemia, hemoglobin M and variants with high oxygen affinity).
 
13. Pregnant or breastfeeding
 
14. Treatment with an investigational drug, biologic, or investigational cardiac implant within 30 days preceding the first dose of study medication or plans to take another investigational drug or biologic within 30 days of study completion
 
15. Other severe, acute, or chronic medical or psychiatric condition or laboratory abnormality that may increase the risk associated with trial participation or investigational product administration or may interfere with the interpretation of trial results and, in the judgment of the Investigator or Sponsor, would make the patient inappropriate for entry into this trial
 
16. Any condition where aerosolized epoprostenol is contraindicated
 
17. Known allergy or sensitivity to epoprostenol, any of its ingredients, or the diluent (glycine)

Study Treatment(s)	
Part I
 
Study treatments are:
 
 • Aerosolized Veletri 50 ng/kg/min administered in accordance with each site's standard of care guidelines • VentaProst Patients who demonstrate at least a 15% improvement in one or more hemodynamic parameters (as defined by the clinical team) with aerosolized Veletri will be crossed over to a calculated VentaProst equivalent dose of 17 ng/kg/min with subsequent dose titration increases of 20% increments (refer to VentaProst Pharmacy Manual) every 15 minutes until a hemodynamic response that is not less than 90% of the effect observed with 50 ng/kg/min aerosolized Veletri is achieved. 
Part II
 
Study treatment is VentaProst at a starting dose of 3.4 ng/kg/min of VentaProst, followed by 3.4 ng/kg/min dose titration increases (refer to VentaProst Pharmacy Manual) every 5 to 15 minutes as clinically indicated until no further improvements in one or more hemodynamic parameters are achieved. VentaProst doses will be decreased to the prior level once a dose response plateau is observed.

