4.6 End of Treatment

In both Part I and Part II, final PD measurements (based on hemodynamic parameters, indices of oxygenation, and ventilator support) will be collected 15 to 30 minutes after discontinuation of VentaProst. End of study physical examination, vital signs/weight, 12-lead ECG, clinical laboratory testing, serum pregnancy testing, hemodynamic parameters, oxygenation measurements, ventilator parameters, adverse events monitoring, and concomitant medications will also be obtained at the end of treatment.

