5.4.1 Criteria for Patient Conversion to Conventional Therapy

At any time during VentaProst administration, patients will be crossed-over to standard of care therapy with aerosolized Veletri if they meet one or more of the following pre-defined criteria for a deterioration in their condition:

- Severe postoperative mediastinal bleeding (> 500 mL/hr)

- Hemoptysis
- If a clinically inadequate response to VentaProst is observed, the patient may be converted back to aerosolized Veletri administered in accordance with each site's standard of care guidelines at the investigator's discretion

Additionally, patients will be crossed-over to standard of care therapy with aerosolized Veletri after extubation.

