6. STUDY TREATMENTS

6.1 Identity of Medication Component of the Investigational Product

The study medication of VentaProst, Flolan (epoprostenol sodium), is manufactured by GlaxoSmithKline and has been analyzed and released according to their specifications. The clinical label will identify the product by name, lot number, Sponsor, storage conditions, and indicate that it is limited to investigational use only.

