6.3.3 Study Medication Administration

6.3.3.1 Part I

Aerosolized Veletri 50 ng/kg/min will be administered to study patients in the OR or the ICU in accordance with each site's standard of care guidelines on administration of aerosolized Veletri. In the ICU, patients who demonstrate a clinically meaningful hemodynamic response (i.e., at least a 15% improvement in one or more hemodynamic parameters) to aerosolized Veletri will be crossed over to a calculated VentaProst equivalent dose of 17 ng/kg/min to be administered through a custom nebulizer delivery system. The VentaProst dose will then be increased in 20% increments (refer to VentaProst Pharmacy Manual) every 15 minutes to match the clinically meaningful PD measures achieved (i.e., not less than 90% of the effect observed) with the aerosolized Veletri dose.

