8.2 Adverse Events

8.2.1 Definitions

Adverse events are any untoward medical occurrence in a patient administered a pharmaceutical product and which does not necessarily have to have a causal relationship with this treatment. For the purposes of this study, this will include unanticipated medical events in the judgment of the investigator. Expected medical events are untoward clinical occurrences that are perceived by the investigator to occur with reasonable frequency in the day-to-day care of patients who have undergone cardiac surgery with CPB and who are treated in the ICU with mechanical ventilation. Such events will not be considered adverse events unless the investigator considers the event to be associated with study medication, study device, or to be unexpectedly severe or frequent for a patient.

A pre-existing condition or symptom is one that is present at the start of the study and is reported as part of the patient's medical history. A pre-existing condition or symptom should be reported as an AE only if its frequency, intensity or character worsens during study treatment.

All AEs that occur from the time of the first dose of study medication through the End of Study will be recorded and reported as Treatment-Emergent Adverse Events (TEAE). All AEs must be appropriately documented in the patient's medical chart and on the CRFs. When known, investigators should report syndromes rather than list symptoms associated with the syndrome.

All AEs that are ongoing at the conclusion of the study should be followed until: a) resolution/stable sequelae; b) the Investigator determines that it is no longer clinically significant; or, c) the study patient is lost to follow-up. If no follow-up is provided, the Investigator must provide a written justification.

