12.6 Extent of Exposure

Exposure data will be summarized by treatment group using frequencies and percentages.

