12.7 Safety Analyses

Safety measurements include AEs, physical examination, vital signs, laboratory tests, and electrocardiograms. Safety data will be summarized by treatment group using frequencies and incidence rates.

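### Adverse events, exposure and the final pharmacodynamic reading are not tied to the epoprostenol product in use, and events after the return to Veletri fall inside the TEAE window

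*Combined protocol and SAP*

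**What the plan says.** Part I patients start on aerosolized Veletri, and responders are switched to VentaProst (Sections 4.1 and 10.1.3). Part II patients start on VentaProst. For both parts, Section 5.4.1 states that "patients will be crossed-over to standard of care therapy with aerosolized Veletri after extubation", and it also provides for conversion on deterioration or inadequate response. The study is open-label (Section 6.5) and has no parallel arms.

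- **Clock.** Section 8.2.1: "All AEs that occur from the time of the first dose of study medication through the End of Study will be recorded and reported" as TEAEs. Sections 8.2.6 and 8.2.7 use the same start for serious events. Sections 10.1.5 and 10.2.4 allow End of Study procedures up to 24 hours after VentaProst stops; Sections 4.3.1 and 4.3.2 give that period as 4 hours or more. Section 12.7.1 defines a TEAE again, comparing treatment with pretreatment and naming neither a product nor an end point.
- **Study medication.** Section 6.1 opens "The study medication of VentaProst, Flolan (epoprostenol sodium" and names no other drug. The Synopsis for Part I has "Study treatments are" and then lists both Veletri and VentaProst. Section 6.3.3.1, which sits under the heading on administering study medication, begins "Aerosolized Veletri 50 ng/kg/min will be administered to study patients in the OR or the ICU".
- **Tables.** Section 12.7: "Safety data will be summarized by treatment group using frequencies and incidence rates". Section 12.6: "Exposure data will be summarized by treatment group using frequencies and percentages". Sections 12.7.1 and 12.7.3 group in the same way. The grouping term is never defined.
- **Final reading.** Section 4.6: the last pharmacodynamic measurements, in both parts, "will be collected 15 to 30 minutes after discontinuation of VentaProst".

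**The concern.** A Part I patient can pass through three periods: Veletri, VentaProst, Veletri again. A Part II patient can pass through the last two. A safety table for VentaProst needs a rule that says which period an event belongs to, and the plan has none. Its one explicit window stays open after the product has changed.

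At stake is the first clinical safety description of VentaProst (Section 2.2.2 reports no earlier trials), based on about 10 patients per part. An event that starts on Veletri after extubation would enter the TEAE count unmarked. A serious event during the Veletri lead-in may fall outside the definition of a serious adverse event, because that definition starts at the first dose of study medication. Counts and percentages do not describe how long, or at what dose, a patient inhaled a titrated drug. The final reading mixes two states unless the report separates them.

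**Working it through.** The plan gives no figure on this point, so there is nothing to reproduce. The check compares definitions and does some short arithmetic.

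**Inputs**
- VentaProst period P = 24 h (Sections 4.3.1 and 4.3.2 say at least this, so it is nominal).
- Tail E, from VentaProst stop to End of Study: 4 h (same sections) to 24 h (Sections 10.1.5 and 10.2.4).
- Final reading at 15 to 30 min (Section 4.6).
- Half-life 2.7 min in animals, about 3 min in vivo (Section 2.1).
- About 10 patients per part (Section 5).

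**1. Where the clock starts.** Section 5 bars study medication for patients who fail any inclusion criterion, and criterion 4c requires a response to Veletri first. Study medication therefore cannot coherently include Veletri. Section 6.1 agrees, and Section 12.3 defines the analysis set by a VentaProst dose. The Synopsis and Section 6.3.3.1 blur this, but the better reading is the first VentaProst dose. On that reading the Veletri lead-in contributes nothing to the TEAE window.

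**2. Where it ends.** Share of the window after VentaProst = E / (P + E).
- E = 4 h: 4 / 28 = 14%.
- E = 24 h: 24 / 48 = 50%.

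This is an upper bound for P = 24 h, because it assumes that the whole tail is spent on Veletri. For a patient fully weaned on the ventilator, the Veletri share is 0%. The share also depends on P. With P = 48 h (assumed) it is 4/52 = 8% to 24/72 = 33%. With P = 12 h (assumed, an early conversion) it is 4/16 = 25% to 24/36 = 67%. These are shares of time; they are shares of events only if the event rate is constant.

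**3. Two definitions.** If treatment in Section 12.7.1 means time on VentaProst, its window is 24 h. The window in Section 8.2.1 is 28 to 48 h, which is 4 to 24 h longer. An event in the tail is a TEAE under one definition and not under the other.

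**4. Grouping.** If treatment group means Part I versus Part II, the products are combined within each part. If it means Veletri versus VentaProst, no rule assigns an event to either. With 10 patients, one patient counted in the wrong column moves an incidence by 1/10 = 10 percentage points.

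**5. Exposure.** The shortest VentaProst course with a completed wean in Part I is 15 min to a first matching reading, a 15 min hold (Section 6.3.4.1), and four 30 min gaps between five downward changes (Section 6.3.5): 15 + 15 + 4 × 30 = 150 min = 2.5 h. Earlier conversion can make it shorter. Against the nominal 24 h, that is 24 / 2.5 = 9.6-fold. A count of patients exposed shows none of this.

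**6. Final reading.** VentaProst-delivered drug remaining = 0.5^(t / half-life).
- 15 min: 2.1% (half-life 2.7 min) to 3.1% (3 min).
- 30 min: 0.05% to 0.10%.

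This applies a systemic half-life to an inhaled drug, so it is approximate. A weaned patient is close to off drug at the reading. A patient already switched is read on Veletri.

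**The case against.** The strongest reply is that most of this is undefined wording in a small, descriptive, open-label study, and that Section 12.1 defers detail to a later SAP. Much of it stands.

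- A reader might infer that Veletri-period data are to be reported as VentaProst data. No section says so. Grouping by product is a permitted reading of treatment group, since the Synopsis names two Part I treatments.
- A reader might also infer that a large part of the Part I TEAEs arises in the Veletri lead-in. The documents point the other way (step 1). Collection also differs by period: Section 10.1.3 asks for unanticipated medical events and Section 10.1.4.1 for adverse events.
- A reader might infer that the Veletri comparison is lost. Section 12.7.1 lists events that are not treatment-emergent, Section 12.3 promises patient listings, and no objective compares event rates between products.
- A reader might infer that the final readings will be pooled, which would dilute a withdrawal effect. No section specifies a pooled summary, and withdrawal effect is not an endpoint. Sections 10.1.4.2 and 10.2.3.2 list the reading among the weaning procedures, which take place on the ventilator.
- Dose times are logged (Section 6.3.1), so hours and dose can be recovered.

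The reply does not reach three points. The TEAE window stays open after the return to Veletri, even on the reading most favourable to the plan. Section 12.6 chooses an exposure summary that does not suit a titrated inhalation. Section 4.6 is general and has no rule for a patient then on Veletri. A later SAP may settle the tables, but it need only be final before database lock, whereas onset times have to be collected during conduct. Section 8.2.7 asks only for an onset date in serious event reports, and a date may not separate two products used on the same day.

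**Conclusion.** The concern holds in a limited form. The plan does not tie adverse events, exposure or the final reading to the product in use. The clearest defect is the end of the TEAE window: after a switch back, 14% to 50% of it can be time on Veletri, given 24 hours on VentaProst, a tail of 4 to 24 hours and Veletri throughout that tail. The share is zero in patients weaned on the ventilator, and the documents do not say how many patients will leave by each route, so no effect on the overall incidence can be given. Part II is affected only through the switch back.

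The conflicting TEAE definitions, the undefined grouping, the exposure summary and the unsplit final reading are secondary but real. None of this shows that the sponsor intends to credit Veletri events to VentaProst; the text simply does not prevent it. The change is worth making because it is cheap and one patient is worth 10 percentage points.

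**What to change.** 1. State in Section 8.2.1 that the TEAE clock starts at the first VentaProst dose. Reconcile Section 12.7.1 with it, including where the window ends, and use study medication consistently in the Synopsis and Section 6.3.3.1.
2. Derive one variable for the product in use at onset: Veletri before, VentaProst, Veletri after, or none. Tabulate adverse events, serious ones included, in separate columns by that variable, and define treatment group accordingly. The lead-in column can be filled only if serious events in that period are collected, which the start point in Section 8.2.6 does not secure.
3. Replace the Section 12.6 summary with hours on VentaProst, maximum dose and cumulative dose, each as median and range.
4. Report the final reading separately for patients off epoprostenol and patients on Veletri, with the number in each.

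The cost is protocol and SAP wording, clock times for adverse event onset and for every dose or product change on the case report form, and the derived variable. With about 10 patients per part the separate columns will be sparse, so they should be read with the listings. Nothing here changes treatment.

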8.2.2 Grading of Adverse Events

The severity of each AE will be categorized using the following criteria:

- Grade 1 (Mild): usually transient; requires no special treatment and does not interfere with the patient's daily activities.
- Grade 2 (Moderate): produces a low level of inconvenience to the patient and may interfere with daily activities. These AEs are usually ameliorated by simple therapeutic measures.
- Grade 3 (Severe): interrupts daily activity and requires systemic drug therapy or other medical treatment.

8.2.3 Relationship to Study Medication/Study Device/Procedure

The Investigator must assess the relationship of each reported AE. The Investigator must make an assessment of the relationship of the AE to the study medication/study device/procedure using the following scale:

- Unrelated: The AE is definitely not or unlikely to be associated with study medication/study device/procedure and is judged due to causes other than the study medication/study device/procedure.
- Related: The AE is possibly or probably related with study medication/study device/procedure.

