8.1.2 Physical Examination

Complete physical examination will include assessments of general appearance; skin and lymphatics; eyes, ears, nose, throat; cardiovascular system; respiratory system; abdomen/gastrointestinal system; urological system; musculoskeletal and neurological systems.

Other body systems may be examined. Clinically significant changes from Screening will be recorded as AEs.

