8.2.5 Laboratory Test and other Test Abnormalities as Adverse Events

A laboratory or other test (ECG, vital signs) abnormality should be reported as an AE if the Investigator considers the abnormality an AE or if the abnormality is associated with accompanying symptoms, requires medical/surgical intervention, leads to a change in study treatment, or results in discontinuation from the trial. When possible, syndromes not laboratory values, should be reported as AEs. For example, elevated hepatic transaminases associated with hepatitis should be reported as “hepatitis” and decreased hemoglobin and hematocrit requiring iron supplementation should be recorded as “anemia.”

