8.2.7 Reporting for SAEs (24 Hours)

Regardless of causality, an SAE must be followed clinically until resolution or stabilization.

All SAEs after the first dose of study medication must be reported to the Sponsor or the Sponsor’s representative within 24 hours of the investigational site’s knowledge of the

occurrence. The investigational site will either telephone the report to the Sponsor's Medical Monitor (contact information found on the Protocol Title Page) or transmit by email a Serious Adverse Event Report (SAER) to the Sponsor's Medical Monitor or the Sponsor's representative. If the initial report is made via telephone, a completed SAER must be emailed within 24 hours of the site's knowledge of the event. Investigational sites will be provided with SAER forms.

The SAE information phoned or emailed to the Sponsor or the Sponsor's representative will include the following (as available):

- Patient Number, Investigator name, and Site Number
- SAE information: event term, onset date, severity, and causal relationship
- Basic demographic information (e.g., age, gender, weight)
- The outcomes attributable to the event (death, a life-threatening adverse drug experience, inpatient hospitalization or prolongation of existing hospitalization, a persistent or significant disability/incapacity, other important medical event[s])
- A summary of relevant test results, pertinent laboratory data, and any other relevant medical history
- The first and last dates of study medication administration
- A statement whether study medication was discontinued or study medication administration schedule modified
- A statement whether event recurred after reintroduction of study medication if administration had been discontinued or withheld
- Supplemental anonymized information may include the following hospital records: laboratory results, radiology reports, progress notes, admission and emergency room notes, holding/observation notes, discharge summaries, autopsy reports, and death certificates

The SAER should be emailed within 24 hours with as much of the above information as available at the time. Supplemental information may be transmitted using a follow-up report and should not delay the initial report.

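### One Related/Unrelated causality rating covers drug, device and an undefined procedure together, so a related AE cannot be attributed to any one of them

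*Combined protocol and SAP*

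**What the plan says.** Section 8.2.3 sets the task: "The Investigator must make an assessment of the relationship of the AE to the study medication/study device/procedure using the following scale". There are two levels. The lower begins "Unrelated: The AE is definitely not or unlikely to be associated with study medication/study device/procedure", and the upper is "Related: The AE is possibly or probably related with study medication/study device/procedure". Neither asks for a rating per component.

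Section 8.2.1 decides earlier whether an event is an AE at all. It describes events that are reasonably common after cardiac surgery with bypass and ventilation in the ICU, and continues: "Such events will not be considered adverse events unless the investigator considers the event to be associated with study medication, study device", or judges them unexpectedly severe or frequent. Procedure is not among the causal targets here.

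Two other sections make events AEs without that exception. On the physical examination, 8.1.2 says "Clinically significant changes from Screening will be recorded as AEs". For test abnormalities, 8.2.5 includes any that "requires medical/surgical intervention, leads to a change in study treatment, or results in discontinuation from the trial".

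For SAEs, 8.2.7 lists among the contents of the report "SAE information: event term, onset date, severity, and causal relationship". Section 12.7.1 plans AE incidence by MedDRA term and treatment group, with no table by relationship or component.

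**The concern.** VentaProst is a drug plus a custom nebulizer system. Section 2.2.2 reports no earlier clinical trial of it, section 6.5 makes the study open-label, and there is no concurrent control group. About 10 patients enter each part, and all have cardiac surgery with bypass. Incidence alone cannot separate product effects from surgical background in such a study, so the investigator's causality judgment carries much of that work.

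A drug effect, a delivery fault and a surgical complication have different consequences for later development. Section 2.2.5 names increased bleeding as a theoretical risk of inhaled epoprostenol, and bleeding may also follow the operation. Under the combined rating both explanations can receive the same label.

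**Working it through.** The plan gives no related-event rate and no calculation to reproduce, so the check is mainly a comparison of sections.

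**1. What the scale can record.** There are three possible targets, each implicated or not: 2 × 2 × 2 = 8 patterns. Reading the slashes as *or*, Unrelated covers one pattern (none implicated) and Related covers the other 8 − 1 = 7. If procedure is set aside, there are 2 × 2 = 4 patterns and Related still covers 3, so drug and device stay merged whatever procedure means.

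**2. What study medication covers.** In Part I the synopsis lists both aerosolized Veletri and VentaProst as study treatments, while section 6.1 applies study medication to the drug in VentaProst. The drug part of the rating does not say which product is meant.

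**3. What procedure covers.** Tables 1 and 2 list the cardiac operation in the column headed Study Procedures. Sections 10.1.2 and 10.2.2 name the operation apart from the study-related procedures. Both readings have support, and sites may differ.

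**4. Which events reach the rating.** Section 8.2.3 rates only reported AEs. Under 8.2.1, an expected post-surgical event becomes an AE if it is linked to drug or device (and is then Related) or is unusually severe or frequent (where surgery may be a possible cause). Sections 8.1.2 and 8.2.5 add examination changes since Screening, which precedes surgery, and abnormalities needing intervention. The example in 8.2.5, a fall in hemoglobin treated with iron and recorded as anemia, could follow from bypass surgery. Some surgical events therefore reach the rating, but by no means all.

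**5. Illustration, with all rates assumed.** Let d be the share of recorded AEs possibly due to drug or device, and q the share possibly due to procedure, taken as independent. Then P(Related) = 1 − (1 − d)(1 − q), and the drug or device share of Related is d / P(Related). With d = 10%:

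- q = 5%: 1 − 0.90 × 0.95 = 14.5% Related; drug or device share 0.10/0.145 = 69%
- q = 20%: 1 − 0.90 × 0.80 = 28%; share 0.10/0.28 = 36%
- q = 50%: 1 − 0.90 × 0.50 = 55%; share 0.10/0.55 = 18%
- q = 90%: 1 − 0.90 × 0.10 = 91%; share 0.10/0.91 = 11%

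The result depends almost wholly on q, which the documents do not give and which the 8.2.1 screen tends to lower. The dilution is anything from slight to severe. The merging in step 1 needs no assumed rate.

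**The case against.** A reader might infer that nearly every complication will be rated Related, because every patient has had surgery, and that counts of related events will be inflated several-fold. The documents do not support this. Section 8.2.1 keeps many routine surgical events from being recorded, so they receive no rating; for these, under-recording by open-label judgment is the likelier problem. The documents also leave open whether procedure means the operation.

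The other side can add that no specified summary uses the rating, so no planned table is distorted. All SAEs are reported within 24 hours and followed regardless of causality (8.2.7). With about 20 patients, other records help: individual listings (12.3), verbatim terms (12.7.1), device replacement reasons and estimated reduced doses (6.4.4, 6.4.5), the dosing history in SAE reports (8.2.7) and data queries to sites (11.3). The AE eCRF page, the SAE report form and the detailed SAP are not among the documents and may already separate the components.

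Most of this stands, and it limits the point to attribution among recorded AEs. It does not remove it. The supporting records allow partial reconstruction case by case, but none is a prespecified judgment on drug versus device, and no section links the device log to AE causality. If the forms already split the rating, the protocol text should say so.

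**Conclusion.** The concern holds in a limited form. Followed as written, 8.2.3 yields a Related entry that does not identify drug, device or procedure, and 8.2.1 and 8.2.3 work from different causal targets. If procedure includes the operation, surgical events that pass the 8.2.1 screen or enter through 8.1.2 or 8.2.5 can also be rated Related. The documents do not allow that extent to be quantified, and no inflation factor should be quoted.

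The conclusion assumes that the slashes mean *or* and that the unseen forms follow the protocol wording. It affects interpretation of safety, a secondary objective. It does not affect the primary endpoint or SAE capture. It is a cheap improvement worth making.

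**What to change.** - In 8.2.3, and in the AE eCRF page and SAE report form if they do not already do so, record separate Related/Unrelated ratings for (a) study drug, specifying VentaProst or Veletri, (b) the VentaProst delivery device, and (c) procedure.
- Define procedure: the cardiac operation, protocol-required procedures, or both.
- Align 8.2.1 with 8.2.3. With separate ratings, the text can state that the causal test for admitting an expected event corresponds to (a) and (b), and that (c) is recorded in addition.
- In 12.7.1 and the SAP, define a treatment-related TEAE as one related to VentaProst drug or device, and show procedure-related events separately in the AE summaries.

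The cost is two extra tick-boxes and slightly more investigator time per AE, plus short wording changes in the protocol and SAP. The split should be in place before data collection, since a judgment not made at the time can be only partly rebuilt from narratives and queries.
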